### 8.2. Study Treatments

For all patients in the study, initial study treatment will consist of a 7-day dose titration regimen. For patients randomized to receive active treatment with RPC1063, this regimen will consist of RPC1063 0.25 mg starting on Day 1 for 4 days, then RPC1063 0.5 mg starting on Day 5 for 3 days, followed by the assigned treatment level beginning on Day 8.

### 8.2.1. Extent of Exposure

Extent of exposure is defined as the total number of days a patient is exposed to any study drug. Because there is no medication diary, the extent of exposure is defined as the total number of days from the first dose date (Day 1) to the last dose date as recorded on the End of Study/Early Withdrawal page on the CRF. If the last dose date on the End of Study/Early Withdrawal page is missing or a patient is lost to follow-up, but the drug accountability log confirms that the patient has taken study drug, the visit date following the last completed drug accountability log will be used.

The extent of exposure and study drug exposure will be summarized in a table by summary statistics for the Safety Population.

The listing will present patient data for the first dose date, last dose date, extent of exposure, and study drug exposure.

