#### Part A

At each visit, previously dispensed study medication capsules will be collected by the Investigator and compliance assessed. Patients will record capsules intake in a dosing diary that will be reviewed periodically by site staff and the Clinical Monitor. Patients exhibiting poor compliance as assessed by medication counts (i.e., 2 or more missed medication days in 1 week) and response to the question "Did you take your medication regularly?" should be counseled on the importance of good compliance to the study dosing regimen. Patients who are persistently non-compliant (< 80% or > 120%) should be discussed with the Medical Monitor to determine whether they should be withdrawn from the study.

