#### Part B

Compliance with IFN  $\beta$ -1a dosing is to be monitored and recorded by site staff. Patients will record IFN  $\beta$ -1a treatment in a dosing diary that will be reviewed periodically by site staff and the Clinical Monitor.

Compliance with RPC1063 capsules will be assessed as described above for Part A.

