# 12.6. Clinical Laboratory Parameters and Abnormal Laboratory Test Results

Clinically significant changes, in the judgment of the Investigator, in laboratory parameters (abnormalities) will be recorded as AEs.

During the treatment period, all Total WBC and WBC differential results will be blinded. If any of the following results are observed, the Investigator will be notified and asked to repeat the laboratory tests:

01 October 2014 Version 4.0

- Absolute lymphocyte count [ALC] < 200 cells/μL
- Absolute neutrophil count [ANC] < 1000 cells/μL
- Total WBC  $> 20,000 \text{ cells/}\mu\text{L}$

If the repeat values also exceed these limits, the Investigator will be informed that the patient's results for the abnormal parameter have fallen outside the acceptable thresholds.

If ANC or total WBC counts are confirmed outside the acceptable limits, the Medical Monitor will contact the treating investigator to request close monitoring for risk of infection and appropriate follow-up, at the discretion of the investigator.

If ALC results are confirmed as below 200 cells/ $\mu$ L, the investigator will be instructed that study drug is to be temporarily discontinued. Laboratory testing will be repeated weekly until the results have returned to within the following acceptable ranges:

• ALC  $> 500 \text{ cells/}\mu\text{L}$ 

When values have returned to acceptable values, the Investigator will be informed that the values are no longer outside of the acceptable range and that study drug may be restarted. (See Section 9.5.1 instructions on resuming treatment after dose interruptions.)

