#### 9.2.1. Analysis

# **Key Secondary Endpoint: The number of new or enlarging hyperintense T2-weighted brain MRI lesions over 24 months**

The primary analysis of the number of new or enlarging T2 hyperintense lesions over 24 months will be performed using a negative binomial regression model adjusted for region, age at Baseline, and Baseline number of GdE lesions, and will include the natural log transformation of the number of available MRI scans as an offset term. The odds ratios and their associated 95% CIs, relative reductions, and p-values will be reported.

The analysis will be repeated in each of the pre-specified subgroups shown in section 5. Forest plots showing the odds ratios and 95% CIs for the overall result and the results in each subgroup will be constructed.

Three sensitivity analyses will be performed: the first will repeat the primary T2 analysis using the mean number of T2 lesions from patients from the same treatment group to impute missing T2 values. The second will repeat the primary T2 analysis using last observation carried forward (LOCF) method for imputing missing T2 data values. Only data from post-Baseline MRI scans can be carried forward to subsequent timepoints for this analysis. The third will repeat the primary T2 analysis using only patients with complete T2 data at the relevant MRI visits (observed cases analysis). All three sensitivity analyses will include the natural log transformation of exposure time on study (instead of the number of available MRI scans) as the offset term.

All T2 lesion results will be listed.

#### Key Secondary Endpoint: The number of GdE brain MRI lesions at Month 24

The number of GdE brain MRI lesions at Month 24 will be analyzed using a negative binomial regression model adjusted for region, age at Baseline, and Baseline number of GdE lesions, and will include the natural log transformation of the number of available MRI scans as an offset term. The odds ratios and their associated 95% CIs, relative reductions, and p-values will be reported.

The analysis will be repeated in each of the pre-specified subgroups shown in section 5. Forest plots showing the odds ratios and 95% CIs for the overall result and the results in each subgroup will be constructed.

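### SAP 8.2.1 justifies its exposure rule by the absence of a medication diary, which the protocol contradicts; the rule counts interruptions as exposure, with a small effect confined mainly to the exposure table and listing

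*SAP*

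**What the plan says.** SAP 8.2.1 states its target first: "Extent of exposure is defined as the total number of days a patient is exposed to any study drug". It then gives the rule and the reason for it: "Because there is no medication diary, the extent of exposure is defined as the total number of days from the first dose date" up to the last dose date on the end-of-study page. Nothing is deducted for time off drug. The same section promises a table and a listing of two quantities, *extent of exposure* and *study drug exposure*, but defines only the first.

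Protocol 9.5.9 describes a diary. The Part A text says: "Patients will record capsules intake in a dosing diary that will be reviewed periodically by site staff and the Clinical Monitor". The Part B text adds: "Compliance with RPC1063 capsules will be assessed as described above for Part A". For the interferon injections, patients record their "treatment in a dosing diary that will be reviewed periodically by site staff and the Clinical Monitor". Table 3 dispenses a diary at Visit 1 and at Visits 3 to 9, and checks drug accountability at Visits 2 to 10. Section 10 asks for dosing times to be entered in the diary around post-dose PK samples.

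The protocol also foresees dosing being stopped and restarted. Under 12.6, if an absolute lymphocyte count (ALC) below 200 cells/µL is confirmed, "the investigator will be instructed that study drug is to be temporarily discontinued". Tests are then repeated weekly, and drug may restart once the count exceeds 500. Section 9.5.1 covers resumption after more than 7 and after more than 14 consecutive missed doses.

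For the T2 endpoint, SAP 9.2.1 says: "All three sensitivity analyses will include the natural log transformation of exposure time on study". The same offset is named for the GdE endpoint. The term is not defined in either place.

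**The concern.** The reason given for the rule does not agree with the protocol, and the rule does not measure what 8.2.1 says it measures. A first-to-last-dose span is treatment duration. It equals days exposed only in a patient who never interrupts dosing.

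The exposure table is where a reader looks to see how much drug each arm received over 24 months. With this rule, a patient held for several weeks and then restarted looks the same as one who was dosed throughout. The drug lowers lymphocyte counts by design and the protocol orders a hold when they fall too far, so the number and length of interruptions by arm are worth reporting. No SAP section asks for them. The undefined offset in 9.2.1 leaves open whether the same span also enters the T2 and GdE sensitivity models.

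**Working it through.** The documents state no exposure figure, so there is nothing to reproduce. The check is direct arithmetic.

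**Inputs.** Visit 10 is Day 729 in Table 3, so a completer dosed from Day 1 to Day 729 has a span of 729 days. The ALC eligibility floor is 800/µL (exclusion criterion 35). The hold limit is a confirmed ALC below 200/µL (12.6). The lymphocyte targets are about 70% reduction at 1 mg and 50% at 0.5 mg (9.2), and the Phase 1 mean change at 1 mg was -71.1% (7.2.4). The share of patients held and the length of holds are not given, so ranges are assumed. A recorded last dose date is also assumed.

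**Direction.** Let S be the span and h the off-drug days inside it. The SAP reports S; days dosed are S - h. Since h is never negative, S cannot fall below the days dosed. A stop that is never followed by a restart ends the span and adds nothing. The stops for AST/ALT, macular edema and FEV1/FVC (9.4.4.1) are of that kind.

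**Size in one patient.** Overstatement = h / (S - h), with S = 729:

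| Gap (days) | Days dosed | Overstatement |
|---|---|---|
| 7 | 722 | 1.0% |
| 14 | 715 | 2.0% |
| 28 | 701 | 4.0% |
| 56 | 673 | 8.3% |
| 91 | 638 | 14.3% |

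**Size in an arm.** If a share p of the arm has one gap of h days, the mean excess is p × h.

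- Low end: 0.01 × 14 = 0.14 days; 0.14 / (729 - 0.14) = 0.02%.
- High end: 0.10 × 91 = 9.1 days; 9.1 / (729 - 9.1) = 1.3%.

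**Scattered missed doses.** At 95% compliance, 0.05 × 729 = 36 days are credited but not dosed. At 80%, 0.20 × 729 = 146 days, and 146 / 583 = 25%.

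**How near the ALC limit is.** From the floor of 800, the Phase 1 mean at 1 mg gives 800 × (1 - 0.711) = 231/µL, and the 50% target at 0.5 mg gives 400/µL. Both are above 200. A fall below 200 from 800 needs a reduction of more than 1 - 200/800 = 75%.

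**What uses the quantity.** The primary relapse model is offset by time on study (SAP 9.1.1). Adverse-event tables count patients (SAP 10.1.1). The main T2 and GdE models are offset by the number of available scans (SAP 9.2.1). That leaves the exposure table and listing and, depending on a definition not given, the T2 and GdE sensitivity models.

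**The case against.** Five arguments can be made for leaving the SAP alone.

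- **Missed doses are reported elsewhere.** SAP 8.2.2 divides capsules taken by capsules expected over the time in study, by arm and in categories, so missed and held capsules lower that rate. This stands in part. It covers capsules only, which are placebo in the interferon arm, and it cannot separate a protocol-ordered hold from non-adherence.
- **A second measure is already listed.** *Study drug exposure* may be intended as the net figure. Without a definition that cannot be known, but the term is a ready place for the correction.
- **No diary may mean no diary dataset.** The SAP is to be read with the case report forms, which are not available here, and 9.5.9 says that site staff and the monitor review the diary, not that daily entries are captured. This stands as a limit on the data source. It does not make the sentence correct, and the accountability log that 8.2.1 itself relies on exists in any case.
- **The rule counts exposure to *any* study drug.** Part B is double-dummy, and 12.6 does not say whether the weekly injection stops with the capsules. If injections continued, the span would be right on its own terms. That stands, but for RPC1063 patients those injections are placebo, so the two products need separate accounting.
- **The error is small.** At arm level this stands.

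A reader might infer that exposure is overstated most where lymphopenia stops the drug, so that the 1 mg arm will look fully exposed despite the most interruptions. The documents do not support that. The patient at the eligibility floor with the mean 1 mg effect reaches 231/µL and does not trigger a hold. No hold frequency is given. A hold lasts at least about 9 days (first weekly retest at 7 plus 2 for central results) or 16 if a second test is needed, whereas ordinary missed doses at 80-95% compliance account for 36 to 146 days. More ALC holds at 1 mg are plausible from the dose targets, but that is inference.

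**Conclusion.** The no-diary statement conflicts with the protocol, and the rule it supports treats off-drug days as exposed days. Both should be corrected. The bias runs one way. It can matter for an individual patient with a long gap, but the mean for an arm is probably overstated by about 1% or less. That figure rests on the assumed range of 1-10% of an arm held once for 14-91 days, and scattered missed doses would add to it. A difference between arms is plausible but cannot be sized from the documents.

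A reader might also infer that safety rates or the primary result are distorted. The SAP specifies no exposure-adjusted adverse-event rate, and the primary offset is time on study, so neither follows. What is lost is an accurate exposure summary, sight of interruptions by arm, and a clear offset in two sets of sensitivity analyses.

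**What to change.** In SAP 8.2.1:

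1. Delete the no-diary statement, or correct it if the meaning is that diary entries are not captured in the database.
2. Label the first-to-last-dose span *treatment duration*.
3. Define *study drug exposure*, already listed in the section, as treatment duration minus recorded off-drug days, separately for capsules and injections. State what counts as off-drug time for a weekly injection. Take the data from accountability logs and recorded interruptions, adding diary data where captured.
4. Summarise the number and length of interruptions by arm, with ordered holds shown apart from other missed doses.

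In SAP 9.2.1, state which quantity is the exposure-time offset in the T2 and GdE sensitivity analyses.

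No dosing, hold or restart rule needs to change for this. The cost is SAP wording and a little programming, largely on data the protocol already requires, and reported exposure will be slightly lower.

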### **8.2.2.** Treatment Compliance

Study drug compliance will be calculated for each patient by taking into account whether a patient takes all doses of study drug as instructed. The study drug compliance rate will be summarized by treatment group using the descriptive statistics for the Safety Population. The overall study drug compliance rate will be calculated by dividing the total number of capsules taken at all visits by the total number of capsules expected for all visits based upon the duration in the study and then multiplying by 100. The number and percentage of patients in each compliance rate category ( $\leq$ 50%, 51-60%, 61-70%, 71-80%, and 81-100%,  $\geq$ 100%,  $\leq$ 80%, and  $\geq$ 120%) will be reported.

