#### Part B

In Part B, patients will be randomized 1:1:1 to receive one of the following 3 regimens:

- IFN β-1a 30 µg IM injection weekly for 24 months
- 0.5 mg RPC1063 oral capsule daily for 24 months
- 1 mg RPC1063 oral capsule daily for 24 months

Dosing will begin following randomization on Day 1.

Part B will be use a double-dummy design. Thus, patients randomized to RPC1063 0.5 or 1 mg will also receive weekly matching placebo IM injections and patients randomized to IFN  $\beta$ -1a 30  $\mu$ g will also receive daily matching placebo oral capsules.

For all patients in Part B, initial study treatment will consist of a 7-day dose titration regimen as shown in Table 7: for patients randomized to receive treatment with RPC1063, this regimen will consist of 0.25 mg RPC1063 starting on Day 1 for 4 days, and 0.5 mg RPC1063 starting on Day 5 for 3 days. All patients will be dosed with their assigned RPC1063 treatment level beginning on Day 8. Patients randomized to IFN  $\beta$ -1a 30  $\mu$ g will receive RPC1063-matching placebo titration kits.

Table 7 Titration Schedule for the RPC1063 Treatment Groups in Part B

	RPC1063/IFN β-1a dose (# RPC1063/Placebo capsules)							
Assigned treatment	Day 1	Days 2 to 4	Days 5 to 7	Day 8*				
RPC1063 0.5 mg	0.25 mg RPC1063 (1 x 0.25 mg capsule) + Placebo	0.25 mg RPC1063 (1 x 0.25 mg capsule)	0.5 mg RPC1063 (2 x 0.25 mg capsules)	0.5 mg RPC1063 (1 x 0.5 capsule) + Placebo IM injection				
RPC1063 1 mg	IM injection  0.25 mg RPC1063  (1 x 0.25 mg  capsule)  +  Placebo  IM injection	0.25 mg RPC1063 (1 x 0.25 mg capsule)	0.5 mg RPC1063 (2 x 0.25 mg capsules)	1 mg RPC1063 (1 x 1 mg capsule) + Placebo IM injection				
IFN β-1a 30 μg	IFN β-1a 30 μg- IM injection + Placebo (1 capsule)	Placebo (1 capsule)	Placebo (2 capsules)	IFN β-1a 30 μg- IM injection + Placebo (1 capsule)				

\* From Day 8 on, patients will continue receiving weekly IM injections (IFN β-1a/ placebo) and daily capsules (RPC1063/placebo) according to the assigned treatment level

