#### 9.5.9. Treatment Compliance

It is the Investigator's responsibility to ensure that patients are correctly instructed on how to take their study medication and that each patient is fully compliant with their assigned dosage regimen. Records of study medication used and intervals between visits will be kept during the study. Drug accountability will be noted by the field monitor during site visits and at the completion of the study. Patients will be asked to return all unused medication at the end of the study. The study treatment should be dispensed by the Investigator, or by a qualified individual under the Investigator's supervision. An up-to-date treatment inventory/dispensing record must be maintained as described above in Section 9.5.5.2.

Overall study non-compliance is defined as taking less than 80% or more than 120% of study medication during the entire treatment period.

Details unique to Parts A or B are described below.

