### 5.3.2. Per-Protocol (PP) Population

The PP population will be a subset from the ITT population with high treatment compliance and without any major protocol deviations. Major protocol deviations will include one or more of the following categories: major inclusion/exclusion criteria violations, poor study drug compliance, and other. The criteria for exclusion from the PP population will include, but are not limited to, those listed below:

- Violation of any of the following three inclusion criteria related to MS specific disease activity:
  - Must have a confirmed diagnosis of MS by the revised 2010 McDonald criteria
  - Must have a Baseline EDSS score between 0 and 5.0
  - Must have at least 1 documented relapse within the last 12 months prior to screening, OR, if at least 1 documented relapse occurred within the last 24 months prior to screening, evidence of at least 1 GdE lesion on brain MRI within the last 12 months prior to randomization
- Poor study drug compliance: compliance up to last dose of study drug <80% The PP population will be fully identified and documented prior to database lock.

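### The SAP's only compliance rate counts capsules, which are placebo in the interferon arm, so recorded injection compliance goes unanalysed

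*SAP*

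**What the plan says.** **Treatment.** Under Protocol 9.5.1 (Part B), patients randomized to interferon "will also receive daily matching placebo oral capsules". The footnote to Table 7 adds that from Day 8 "patients will continue receiving weekly IM injections", active or placebo, alongside the daily capsules. Every patient therefore has two components, and only one of them is active.

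**Compliance rate.** SAP 8.2.2 obtains the overall rate by "dividing the total number of capsules taken at all visits by the total number of capsules expected for all visits", multiplies by 100 and summarises it by treatment group. There is no injection term, and no other compliance calculation appears in the visible SAP.

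**Per-protocol set.** SAP 5.3.2 lists as an exclusion "Poor study drug compliance: compliance up to last dose of study drug <80" (percent). It does not say which component is meant.

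**What is collected.** Protocol 9.5.9 (Part B) states that compliance with interferon "dosing is to be monitored and recorded by site staff", and that patients also enter this treatment in a dosing diary. For capsules, Part B follows the Part A text of the same section: "Patients will record capsules intake in a dosing diary". Protocol 9.5.5.2 requires an accountability record for each patient. Table 3 has the patient diary dispensed from baseline and a compliance check at each post-baseline visit.

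**Diary.** SAP 8.2.1 bases its exposure definition on the opposite premise: "Because there is no medication diary".

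**The concern.** One number carries two meanings. In the two RPC1063 arms the capsule rate measures intake of active drug. In the interferon arm it measures intake of placebo. A table that sets these side by side by treatment group invites a comparison that it cannot support. SAP 8.2.2 itself opens by saying that compliance reflects whether all doses of study drug were taken as instructed, and a capsule count cannot show that for a patient who also has a weekly injection.

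This matters because Part B tests superiority over interferon. A reader of a positive result will ask whether the comparator was actually taken. The protocol gives grounds for the question: section 7.3 names compliance among the difficulties of injectable therapies, and section 9.5.1 has patients self-inject without supervision after the first dose. The planned compliance table cannot answer it. If the per-protocol cut-off uses the same ratio, it would also select patients on active-drug adherence in two arms and on placebo adherence in the third.

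**Working it through.** The plan states no figure to reproduce, because the point concerns a definition. The check applies the SAP 8.2.2 ratio to a full course.

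**Inputs**
- Duration: Month 24 is Week 104 (Protocol Table 3), so 104 × 7 = 728 dosing days. Full completion is assumed.
- Capsules: one a day, with two a day on Days 5 to 7 (Protocol Table 7). Expected: 728 + 3 = 731.
- Injections: weekly from Day 1. Expected: 728 / 7 = 104.
- Cut-off: below 80% (SAP 5.3.2).

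**Interferon patient who takes all 731 placebo capsules**

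| Injections taken | SAP rate (capsules only) | Injection rate | Pooled rate |
|---|---|---|---|
| 0 of 104 | 731/731 = 100% | 0% | 731/835 = 87.5% |
| 26 of 104 | 100% | 25% | 757/835 = 90.7% |
| 52 of 104 | 100% | 50% | 783/835 = 93.8% |
| 104 of 104 | 100% | 100% | 835/835 = 100% |

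The SAP rate is the same in every row, so it carries no information on interferon intake.

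**The reverse case.** 80% of 731 is 584.8. An interferon patient who takes all 104 injections but only 584 placebo capsules scores 584/731 = 79.9% and, if the cut-off uses the capsule ratio, fails it despite full active treatment.

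**Pooling.** One ratio over both components has a denominator of 731 + 104 = 835, of which injections are 104/835 = 12.5%. Missing all of them leaves 87.5%, still above 80%, so pooling does not solve the problem.

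**A separate injection rate.** 80% of 104 is 83.2, so at least 84 injections are needed. A patient who misses 20 has 84/104 = 80.8% and passes; one who misses 21 has 83/104 = 79.8% and fails. This rate tells the four rows of the table apart.

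**Diary.** SAP 8.2.1 denies that a medication diary exists. Protocol 9.5.9 describes one for capsules and for interferon injections, and Table 3 has it dispensed. The two documents cannot both be right.

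**The case against.** Several stronger readings are tempting, and the documents do not support them.

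- **A reader might infer that interferon compliance is never measured.** Protocol 9.5.9 and 9.5.5.2 require it to be monitored, recorded and accounted for. The gap lies in the SAP's analysis, not in data collection.
- **A reader might infer that a patient who skips every injection necessarily stays in the per-protocol set.** SAP 5.3.2 says study drug, not capsules, describes its list of criteria as not exhaustive, and has membership documented before database lock. Such a patient could still be excluded as a major deviation. That the cut-off uses capsules is an inference, drawn because SAP 8.2.2 holds the only compliance formula.
- **A reader might infer that the superiority result is at risk.** SAP 5.3.1 makes ITT the primary population for all efficacy endpoints. The visible SAP uses the per-protocol set only for disposition and for demographic and baseline summaries, so no visible efficacy estimate or p-value depends on the rule.
- **A reader might infer that an under-treated comparator would be invisible.** Extent of exposure, discontinuations, adverse events leading to permanent discontinuation and protocol deviations are all reported by other routes. They would show part of the problem, although none gives an injection rate.
- **A reader might infer that the per-protocol rule must adopt the upper limit in Protocol 9.5.9, which defines non-compliance as "taking less than 80% or more than 120% of study medication".** That passage does not define the per-protocol set, and Protocol 13.5 leaves its criteria to the SAP. Adding the upper limit is a matter of preference.

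It can also be said that diary entries may never reach the database, since the protocol says only that staff and the monitor review them. That stands as a practical caution about the fix. None of these objections removes the central fact that the tabulated rate for the interferon arm is a placebo rate.

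**Conclusion.** The point holds in a limited form. The SAP's compliance rate is wrong for the comparator as written, not merely under-described: for about 400 interferon patients it carries no information on up to 104 scheduled injections each. By inference the same ratio drives the 80% per-protocol cut-off, and SAP 5.3.2 should settle this either way. The consequence falls on the compliance table and on per-protocol membership, and does not reach the ITT primary analysis.

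The conclusion on the compliance table follows from the formula and the double-dummy design alone. The counts of 731 and 104, and the 87.5% pooled figure, assume a full 24-month course; a shorter course changes the counts but not the argument. The statement that no per-protocol efficacy analysis is planned rests on the visible text of the SAP.

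**What to change.** 1. **SAP 8.2.2:** define two rates, capsules taken over capsules expected and injections taken over injections expected. Compute both in every arm from site dosing and accountability records, using the diary where it is captured. Report both by arm and do not pool them.
2. **SAP 5.3.2:** state that the 80% cut-off applies to each component separately in every arm. A rule based on the active component alone (injections for interferon, capsules for RPC1063) would need the treatment codes, whereas Protocol 13.5 requires per-protocol membership to be settled before unblinding. The component-wise rule needs no codes.
3. **SAP 8.2.1:** reconcile the no-diary premise with Protocol 9.5.9 and state which source supplies the dosing data.

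The cost is SAP wording and a modest amount of programming. The team must first confirm that injection records reach the database in usable form, because the documents do not show this for diary entries. The per-protocol set may become slightly smaller, since patients who are non-compliant with their placebo component alone would also be excluded. That is the price of a rule that can be applied blind.
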